The results of the Canadian SR-2 study, where patients were randomised to receive preoperative or post-operative radiotherapy were interesting. Those treated with pre-operative radiotherapy received 50Gy in 25 fractions as opposed to 66Gy in 33 fractions for the postoperative group. The study was stopped after a planned interim analysis showed that there was a statistically significant increase in wound complication rate in the pre-operative arm. This increased complication rate was confined to those patients with tumours in the thigh. The completion of the study to planned size would not have resulted in a non-statistically significant result.

A correlation was observed with bone toxicity and the TESS score. Maximal radiation dose and Musculo Skeletal Tumour Rating Scale (MSTS) were associated with joint toxicity and field area was associated with oedema. Results from this study suggest that both field area and total dose are contributory factors to greater subcutaneous tissue toxicity and oedema and that both dose and field size are important in determining morbidity and function following a combination of surgery and radiotherapy in extremity sarcoma. This study also confirmed that the use of pre-operative radiotherapy in general results in use of smaller radiotherapy fields. A proportion of the patients in this trial did receive a post operative boost where the surgical margin was poor but on average the total dose received was also lower in the pre-operative radiotherapy arm. This has previously been demonstrated by (Nielsen et al; 1991) and (Robinson et al; 1991).

Long term follow-up of the functional consequences and morbidity of the two treatment arms has been reported. These were compared using the RTOG scores for toxicity to skin and subcutaneous tissue, bone, joint stiffness and oedema and by evaluating a relationship of these endpoints to function as measured by the Musculo Skeletal Tumour Rating Scale (MSTS) and the Toronto Extremity Salvage Score (TESS) 2 years post treatment. Significantly more patients in the post operative arm had grade 2 or greater subcutaneous fibrosis, more frequent oedema and joint stiffness. Field size was predictive of greater rates of fibrosis and joint stiffness and marginally predictive of oedema. Fibrosis, joint stiffness and oedema adversely affect patient function (Davis *et al;* 2004).

Surgical margins and radiotherapy dose

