2. OBJECTIVES

The objective of this trial is to assess if a reduced volume of post-operative radiotherapy increases limb function without compromising local control.

Outcome Measures

Primary outcome measures

- Limb functionality: as measured by the Toronto Extremity Salvage Score (TESS).
- Time to local recurrence: defined in whole days, as the time from randomisation into the trial to the occasion when a local recurrence is confirmed by biopsy. For those patients who are not observed to have a local recurrence during the course of the study, the time to local recurrence will be censored at the last follow-up date.

Secondary outcome measures

- Soft tissue and bone toxicity: measured by the RTOG scoring system.
- **Disease-free survival time:** defined in whole days as time from randomisation into the trial to either local or distant recurrence or death (whichever occurs first).
- Overall survival time: defined in whole days as time from randomisation into the trial to death.
- Overall level of disability: as measured using the two general questions on the TESS questionnaire.

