6. STATISTICAL CONSIDERATIONS

Analysis of outcome measures

The primary research hypothesis for the trial is that a reduced volume of post-operative radiotherapy treatment for adult extremity soft tissue sarcomas will improve limb function without compromising local control. Secondary research hypotheses are that the reduced treatment improves toxicity, overall level of disability and is not inferior to the standard treatment in terms of disease-free survival and overall survival.

The primary analysis for the trial is to compare the experimental treatment to the control treatment in terms of benefit to limb function and non-inferiority for time to local recurrence. For limb function, TESS will be analysed using longitudinal statistical methods, in particular summary measures analysis. The two treatment groups will be compared in terms of TESS at 2 years and area under the curve using either t-tests or Wilcoxon tests depending on the distribution of the data. The proportion of patients in each treatment arm who report small, medium or large change (with worsening or improvement reported separately) between each assessment interval will be required. For time to local relapse, statistical analysis will be based on a one-sided 95% confidence interval for the hazard ratio and non-inferiority will be inferred when the entire confidence interval falls above the non-inferiority margin of 0.63 (equivalent to a difference of 80% versus 70% in 2-year local relapse-free rates).

The rates of grade 3 or 4 toxicity on the two treatment arms will be compared using chisquare tests. Overall level of disability will be analysed using longitudinal statistical methods similar to those used for TESS. Statistical analysis for disease-free survival and overall survival will be based on one-sided 95% confidence intervals for the hazard ratio to assess non-inferiority.

Interim analysis

Interim analyses will be carried out annually and presented to an independent Data Monitoring Committee (DMC). The interim analyses will present recruitment data and data on all primary and secondary outcomes.

Final analysis

The study is expected to complete recruitment within 4 years. Final analysis will be carried out after all patients have been followed up for a minimum of two years.

Calculation of sample size

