9. SAFETY REPORTING

Definition of an Adverse Event (AE)

An Adverse Event (AE) is any unfavourable and unintended sign (including an abnormal laboratory finding), symptom or disease temporarily associated with the use of a medical treatment or procedure regardless of whether it is considered related to the medical treatment or procedure (attribution of unrelated, unlikely, possible, probable, or definite).

Definition of a Serious Adverse Event (SAE)

An SAE is defined as any untoward and unexpected occurrence that:

- a) Results in death
- b) Is life-threatening* (at the time of the event);
- c) Requires inpatient hospitalisation or prolongation of existing hospitalisation**;
- d) Results in persistent or significant disability or incapacity;
- e) Consists of a congenital anomaly or birth defect;

*The term 'life threatening' in the definition of 'serious' refers to an event in which the patient was at risk of death at the time of the event; it does not refer to an event that hypothetically might have caused death if it were more severe.

**Hospitalisation is defined as an in-patient admission, regardless of length of stay, even if the hospitalisation is a precautionary measure, for continued observation. Hospitalisation for pre-existing condition, including elective procedures, which has not worsened, does not constitute a serious adverse event.

NCI Common Toxicity Criteria for Adverse Events

This study will collect adverse events using the Common Toxicity Criteria for Adverse Events (CTCAE) version 3.0. An electronic version may be accessed through the web at http://ctep.cancer.gov/. The CTCAE (Version 3.0) provides a descriptive terminology that is to be used for adverse event reporting. A grading (severity) scale is also provided in the CTCAE for each adverse event term.

[figure not shown]
Expected and Unexpected Events

The following events associated with radiation treatment are anticipated. Refer to the NCI CTCAE for grading criteria of AEs.

The following table provides the expected adverse events:

Adverse Events					
Incidence between 50%-95%	Incidence between 10%-20%	Incidence 5% or less			
skeletal muscle fibrosis	moist desquamation	anorexia			
erythema	lymphoedema	insufficiency fracture			
epilation	dry skin	osteoporosis			
pigmentation/depigmentation	nausea	radiation induced malignancy			
induration	aesthenia	peripheral nerve fibrosis			
Joint stiffness/immobility		brachial/sciatic nerve plexopathy			
dry desquamation		diarrhoea			

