17. TRANSLATIONAL RESEARCH: VORTEX -BIOBANK

All patients enrolled in VORTEX will be invited to participate in VORTEX-BIOBANK.

Only those patients, who have consented to further research using their tumour and normal tissue samples and blood will be entered for analysis in this study. Patients have the right to participate in the VORTEX without participating in the translational research.

The biobank will be established in Manchester.

Objectives

The ability to determine early in the course of treatment patients with an increased likelihood of distant metastases would highlight individuals who might benefit from early adjuvant systemic therapy.

Translational hypothesis

The translational hypothesis is that a pre-treatment tumour molecular profile (RNA or protein) will define patients with a high risk of treatment failure following surgery and post-operative radiotherapy, and that the profile could be used in a subsequent study to identify patients who might benefit from adjuvant systemic therapy such as a hypoxia targeted agent.

Secondary hypothesis

Is that a single nucleotide polymporphisms (SNPs) in candidate genes will predict patients with a high risk of radiation side-effects, specifically limb functionality (TESS) and the level of ≥grade 2 fibrosis measured using the RTOG scale.

Specimen collection and banking

- Tumour and normal tissue samples will be taken at the time of surgery and placed in RNAlater for future microarray analyses. Tumour samples will be taken in triplicate. It is envisaged that a single normal tissue sample will be obtained from at least half of the patients. Once the tumour is clamped/removed there is a 30 minutes window for sampling the tissue and submerging in the reagent i.e. RNAlater or formalin as appropriate. The theatre nurse will take the samples and place them in the microtubes.
- The microtubes containing tissue samples must remain upright, at room temperature and held overnight in a safe area prior to posting the following day to the VORTEX-BIOBANK office.
- In Manchester, the samples are logged and placed at -80°C for storage until ready to prepare the RNA microarrays.

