Appendix 3: RTOG/EORTC Late Radiation Morbidity Scoring Schema

ORGAN TISSUE	0	Grade 1	Grade 2	Grade 3	Grade 4	
SKIN	None	Slight atrophy Pigmentation change Some hair loss	Patch atrophy; Moderate telangiectasia; Total hair loss	Marked atrophy; Gross telangiectasia	Ulceration	
SUBCUTAN EOUS TISSUE	None	Slight induration (fibrosia) and loss of subcutaneous fat	Moderate fibrosis but asymptomatic Slight field contracture <10% linear reduction	Severe induration and loss of subcutaneous tissue Field contracture >10% linear measurement	Necrosis	
BONE	None	Asymptomatic No growth retardation Reduced bone density	Moderate pain or tenderness Growth retardation Irregular bone sclerosis	Severe pain or tenderness Complete arrest of bone growth Dense bone sclerosis	Necrosis/ Spontaneous fracture	
JOINT	None	Mild joint stiffness Slight limitation of movement	Moderate stiffness Intermittent or moderate joint pain Moderate limitation of movement	Severe joint stiffness Pain with severe limitation of movement	Necrosis/ Complete fixation	

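### The stated toxicity comparison, grade 3 or 4 by chi-square, is valid but insensitive for the hypothesis that reduced volume improves toxicity; an ordinal or grade 2+ comparison should be pre-specified beside it

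*Protocol*

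**What the plan says.** Section 6 of the protocol sets out the hypothesis: "Secondary research hypotheses are that the reduced treatment improves toxicity, overall level of disability". The same section gives the analysis: "The rates of grade 3 or 4 toxicity on the two treatment arms will be compared using chisquare tests". No other comparison of toxicity between the arms is stated.

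The analysis sentence names neither the scale nor the period. Section 2 lists soft tissue and bone toxicity as a secondary outcome, "measured by the RTOG scoring system", so I read the sentence as referring to RTOG late morbidity. Appendix 3 grades skin, subcutaneous tissue, bone and joint from 0 to 4. The schedule of events in Section 3 has late morbidity assessed at 6 months and at each later visit.

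Elsewhere the protocol works at a lower cut. The introduction reports, from the earlier randomised trial of pre- against post-operative radiotherapy: "Significantly more patients in the post operative arm had grade 2 or greater subcutaneous fibrosis, more frequent oedema and joint stiffness". The secondary biobank hypothesis in Section 17 uses "the level of ≥grade 2 fibrosis measured using the RTOG scale".

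**The concern.** A split between grades 2 and 3 treats grades 0, 1 and 2 as the same outcome. It also tests the hypothesis where events are likely to be fewest. The sample size in Section 6 rests on TESS and local relapse, so nothing in the plan secures power for toxicity.

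If smaller fields mainly move patients from moderate to mild or no morbidity, the stated test can easily miss it. A non-significant result would then say little about whether the reduced volume lowers toxicity, although the protocol's own background describes morbidity at grade 2 or more. An ordinal or grade 2+ analysis first introduced after the arm-level data are known would look data-driven, so it is better fixed beforehand.

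**Working it through.** **The plan's own figures.** Both stated sample sizes reproduce.
- TESS (difference 10, SD 20, two-sided 5%, power 95%): n = 2 × (1.960 + 1.645)² × 20² / 10² ≈ 104 per arm, against 105 stated.
- Local relapse (80% in both arms, margin 10 points, one-sided 5%, power 80%): n = (1.645 + 0.842)² × (0.16 + 0.16) / 0.10² ≈ 198 per arm, as stated.

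Neither concerns toxicity. The protocol gives no toxicity power and no rate by RTOG grade. Its table of expected adverse events in Section 9 puts fibrosis, induration and joint stiffness in a 50% to 95% band, but without a grade.

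**Assumed inputs.** 180 assessable patients per arm (200 planned), two-sided 5%, the same odds ratio of 0.6 at every cut, and control rates of grade 2+/3+ of 30%/5%, 40%/10% and 50%/15%.

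**Formula for each cut.** With control rate p₁:
- p₂ = 0.6·o / (1 + 0.6·o), where o = p₁/(1 − p₁)
- power = Φ{[|p₁ − p₂|√n − 1.96√(2p̄(1 − p̄))] / √(p₁(1 − p₁) + p₂(1 − p₂))}, where p̄ is the mean of p₁ and p₂

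*Grade 3+, control 10%.* o = 0.1111 and p₂ = 0.0667/1.0667 = 0.0625. Then (0.0375 × 13.416 − 1.96 × 0.3864)/0.3855 = −0.66, so power is 25%.

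*Grade 2+, control 40%.* o = 0.6667 and p₂ = 0.4/1.4 = 0.2857. Then (0.1143 × 13.416 − 1.96 × 0.6713)/0.6664 = 0.33, so power is 63%.

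| Control grade 2+ / 3+ | Chi-square, grade 3+ | Chi-square, grade 2+ | Rank test on grades 0 to 4 |
|---|---|---|---|
| 30% / 5% | 15% | 55% | 61% to 74% |
| 40% / 10% | 25% | 63% | 67% to 76% |
| 50% / 15% | 35% | 67% | 72% to 76% |

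The chi-square columns come from the formula. Simulation agrees, with grade 3+ power between about 13% and 35%. The rank-test column is simulated under proportional odds. Its range comes from varying the control rate of grade 1 or more, from 5 points above the grade 2+ rate up to 90%.

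**Other effect sizes, 200 per arm** (control grade 3+ of 3% to 15%, grade 2+ of 30% to 50%):
- odds ratio 0.5: 17% to 58% at grade 3+, 83% to 93% at grade 2+
- odds ratio 0.67: 9% to 26% at grade 3+, 42% to 51% at grade 2+

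**Detectable effect, 200 per arm, 80% power.** At grade 3+ the rate must fall from 10% to about 3%, or from 15% to about 6.4%. At grade 2+ a fall from 40% to about 27% is enough.

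**Information kept by a cut**, relative to a proportional-odds analysis of all grades: p(1 − p) / [(1 − Σpₖ³)/3]. For assumed proportions in grades 0 to 4 of 0.15, 0.40, 0.30, 0.12 and 0.03, Σpₖ³ = 0.0961 and the denominator is 0.3013. Grade 3+ keeps 0.15 × 0.85/0.3013 = 42%, and grade 2+ keeps 0.45 × 0.55/0.3013 = 82%. Over three assumed distributions, with grade 3+ at 7%, 15% and 20%, the grade 3+ cut keeps 22%, 42% and 53%. The grade 2+ cut keeps 78% to 82%.

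**Reverse case.** If the odds ratio of 0.6 applies only at grade 3 and above and the grade 2+ rate does not change, the rank test has about 5% to 8% power, against 15% to 36% for the protocol's chi-square.

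**The case against.** Grade 3 or 4 is a conventional and clinically meaningful cut. Appendix 3 describes grade 2 subcutaneous toxicity as "Moderate fibrosis but asymptomatic", and the functional effect of milder morbidity is already measured by TESS, a primary outcome. The ordinal gain is computed under proportional odds, the model that favours the ordinal test, and the reverse case shows that replacing the severe cut could lose power for severe harm. The protocol does not rule out further analyses, and a separate analysis plan may add them.

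Most of this stands, and it defeats a replacement. It does not defeat an addition. Grade 2 is not asymptomatic throughout: in Appendix 3, grade 2 bone toxicity includes moderate pain and grade 2 joint toxicity includes moderate stiffness and pain. The grade 3 or 4 comparison is also a choice the protocol itself fixes, not a detail it leaves open.

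Three stronger readings are tempting and are not supported.
- *That the field-size evidence is at grade 2 or more.* The grade 2 threshold belongs to the comparison of pre- with post-operative arms, where dose also differed (50 against 66 Gy). The field-size sentence, "Field size was predictive of greater rates of fibrosis and joint stiffness and marginally predictive of oedema", gives no grade.
- *That most of the information is thrown away.* The documents give no rates from which to derive this. Under the assumptions above the loss is 47% to 78%, and in one of the three distributions it is under half. Every grade is still recorded.
- *That the results could not be set beside the earlier trial or the biobank endpoint.* Grade 2+ proportions can be tabulated from the same records. The biobank hypothesis concerns prediction of a patient's risk, so its cut need not match the randomised comparison.

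**Conclusion.** The point holds as one of sensitivity. The only toxicity comparison the protocol states is valid, but it has low power for the hypothesis it serves and sits one grade above the threshold used in the protocol's own fibrosis evidence and biobank endpoint. Under the base assumptions its power is about 13% to 35%, against 55% to 67% at grade 2 or more and roughly 60% to 76% for an ordinal test, depending on the split between grades 0 and 1.

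These figures rest on assumed rates and on an effect shared across grades; the advantage disappears if the effect lies only at grade 3 or 4. The matter concerns a secondary outcome on which the trial was not sized. It is a cheap improvement, and the primary conclusions on limb function and local recurrence do not depend on it.

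**What to change.** Keep the grade 3 or 4 comparison as it stands. Beside it, pre-specify for each tissue in Appendix 3 (skin, subcutaneous, bone, joint) a comparison of late RTOG grade as an ordered 0 to 4 outcome, by Wilcoxon test or proportional-odds model, and report the grade 2+ proportions by arm. Fix the time: either the grade at 24 months or the worst grade from 6 to 24 months. Follow-up is open-ended and unequal, so a worst grade without a window would depend on how long each patient was observed. Settle this before toxicity results by arm are known.

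The cost is some extra analysis, with no new visits, forms or patients. There are two downsides. Four tissues bring several more secondary tests, so the added results should be labelled supportive. A shift within grades 1 and 2 also carries less clinical weight than one in severe toxicity, so it should always be shown together with the grade 3 or 4 rates.

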Local recurrences must be confirmed histologically. It is vital that a detailed record – photographic and imaging (MRI) of the site of local recurrence is documented. In particular the relationship to the radiotherapy fields must be ascertained. Patient management thereafter is at the discretion of the treating clinicians.

FOLLOW-UP EVALUATIONS

3 months post -operation

- -Performance Status
- -Wound assessment
- -Chest X-ray
- -Completion of the Toronto Extremity Salvage Score (TESS) questionnaire
- -Completion of the Patient perceived change of status

6 months post-operation

- -Performance Status
- -Late radiation morbidity
- -Wound assessment
- -Chest X-ray
- -Completion of the Toronto Extremity Salvage Score (TESS) questionnaire
- -Completion of the Patient perceived change of status

9 months post-operation

- -Performance Status
- -Late radiation morbidity
- -Chest X-ray

12 months post-operation

- -Performance Status
- -Late radiation morbidity
- -Chest X-ray
- -MRI local site
- -Completion of the Toronto Extremity Salvage Score (TESS) questionnaire
- -Completion of the Patient perceived change of status

15 months post-operation

- -Performance Status
- -Late radiation morbidity
- -Chest X-ray

18 months post-operation

- -Performance Status
- -Late radiation morbidity
- -Chest X-ray
- -Completion of the Toronto Extremity Salvage Score (TESS) questionnaire
- -Completion of the Patient perceived change of status

21 months post-operation

- -Performance Status
- -Late radiation morbidity
- -Chest X-ray

24 months post-operation

- -Performance Status
- -Late radiation morbidity
- -Chest X-ray
- -MRI local site
- -Completion of the Toronto Extremity Salvage Score (TESS) questionnaire
- -Completion of the Patient perceived change of status

Six monthly from 24 months to 5 years

- -Performance Status
- -Late radiation morbidity
- -Chest X-ray

Annually from 5 years

- -Performance status
- -Late radiation morbidity
- -Chest X-ray

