Sample size calculations are based on the two primary outcome measures of limb function and time to local recurrence. In relation to limb function, a difference in TESS score between the two treatment arms of 10 points would indicate a clinical benefit to patients (Davis, personal communication). Previous data has suggested an expected standard deviation for the score of 20. The key analysis for this outcome measure is the difference in score at two years. Assuming a null hypothesis of no difference will be tested using a t-test with 5% significance level and assuming a standard deviation of 20, 105 patients per treatment arm will be needed to detect this size of difference at two years with 95% power.

In relation to local relapse, sample size is calculated based on showing that the 2-year local relapse rate on the experimental treatment arm is non-inferior to that on the control arm. The two-year local relapse-free rate on the control treatment is expected to be 80% and a decrease in this rate to 70% would be the largest difference between treatments that can be judged as clinically acceptable. A non-inferiority margin of 70% is therefore chosen as relevant for this trial. With 198 patients per arm with full follow-up for two years and using a one-sided 95% confidence interval there will be 80% power to detect non-inferiority in two-year local relapse-free rates of 10% or less.

In conclusion, with 200 patients per treatment arm, there will be 95% power to detect a difference of 10 points in the TESS score between the treatment arms at two years and 80% power to determine non-inferiority in local relapse-free rates with non-inferiority defined as a difference in two-year local relapse-free rates of 10%.

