8. MILESTONES

The anticipated schedule is as follows:

March 2006 Open trial to recruitment

March 2010 400 patients recruited; close trial to recruitment

March 2012 Final analysis

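### Late grade 3–4 toxicity is compared by a chi-square test of rates with no assessment time, although scoring spans about 2 to 6 years of potential follow-up that ends at death

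*Protocol*

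**What the plan says.** Protocol section 2 lists the secondary outcome as "Soft tissue and bone toxicity: measured by the RTOG scoring system", with no time point. Section 6 (Analysis of outcome measures) states the hypothesis it serves: "Secondary research hypotheses are that the reduced treatment improves toxicity, overall level of disability". The comparison is then fixed in one sentence: "The rates of grade 3 or 4 toxicity on the two treatment arms will be compared using chisquare tests".

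The other outcomes in that section are tied to time. TESS is compared at 2 years and as an area under the curve. Local relapse, disease-free survival and overall survival are analysed through hazard ratios.

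On duration, section 6 says "The study is expected to complete recruitment within 4 years" and "Final analysis will be carried out after all patients have been followed up for a minimum of two years". Section 8 (Milestones) opens recruitment in March 2006, closes it in March 2010 and places the final analysis in March 2012. The follow-up schedule in section 5 scores late radiation morbidity from 6 months after operation, every three months to 24 months, every six months to 5 years and yearly after that. After a local recurrence, section 5 says "Patient management thereafter is at the discretion of the treating clinicians".

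**The concern.** Late radiation morbidity accumulates over years, so the chance of having recorded a grade 3 or 4 event depends on how long a patient was observed. A chi-square test on whether an event was ever recorded treats a patient who died at eight months as toxicity-free, on a par with one seen for six years.

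There are two consequences.

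- **Interpretation.** The percentage mixes patients with about 2 years and about 6 years of potential follow-up. It is the risk at no stated time. It also drifts upward between the annual interim analyses, which cover the secondary outcomes.
- **Validity of the test.** Randomisation balances calendar follow-up. It does not balance observation cut short by death or loss if those differ between arms. The arm observed for less time then shows fewer events with no true difference in toxicity. If that were the reduced-volume arm, the error would favour the hypothesis the trial hopes to support.

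**Working it through.** **The protocol's figures.** No number is given for the toxicity comparison. The relapse figures that bound the scenarios do reproduce: ln(0.80)/ln(0.70) = 0.626, the stated margin of 0.63. Potential follow-up runs from March 2010 to March 2012 = 2 years for the last patient, up to March 2006 to March 2012 = 6 years for the first.

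**Inputs from the protocol.** 200 patients per arm; follow-up of 2 to 6 years; 80% v 70% two-year local relapse-free rates, the second described thus: "a decrease in this rate to 70% would be the largest difference between treatments that can be judged as clinically acceptable".

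**Assumptions not in the protocol.** Uniform entry, constant hazards, the same toxicity hazard λt in both arms (5% or 10% per year), and a hazard λs of observation ending that corresponds to the stated two-year rate:

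- 80%: λs = −ln(0.80)/2 = 0.1116
- 75%: λs = −ln(0.75)/2 = 0.1438
- 70%: λs = −ln(0.70)/2 = 0.1783

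**Step 1: what the percentage means.** With λt = 0.05 and nobody lost, true risk is 1 − e^(−0.10) = 9.5% at 2 years and 1 − e^(−0.30) = 26% at 6 years. The proportion over all follow-up is 1 − [e^(−0.10) − e^(−0.30)]/(4 × 0.05) = 18%. With observation ending at λs = 0.1116 it falls to 14%.

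**Step 2: expected proportions with no toxicity effect.** With s = λt + λs,

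p = (λt/s) × {1 − [e^(−2s) − e^(−6s)]/(4s)}.

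| λt per year | 80% arm | 70% arm | Spurious difference |
|---|---|---|---|
| 5% | 14.4% | 12.8% | 1.6 points |
| 10% | 26.4% | 23.5% | 2.9 points |

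**Step 3: two-sided type I error at 200 per arm** (normal approximation and simulation agree closely).

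| Still observed at 2 years | Chi-square, all follow-up | Log-rank, time to first event |
|---|---|---|
| 80% v 80% | about 5% | about 5% |
| 80% v 75% | about 6% | about 5% |
| 80% v 70% | 7.6% to about 10% | about 5% |

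The first row shows that the 2-to-6-year spread does no harm to the test when loss is equal.

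**Step 4: a chi-square test fixed at 2 years**, for 80% v 70%, using p = (λt/s) × (1 − e^(−2s)). The proportions are 8.5% v 8.0% and 16.3% v 15.3%, with rejection of 5.4% and 5.8%. Nearly all the bias goes.

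**Step 5: power** with equal loss and a true hazard ratio of 0.6, at the two toxicity hazards (simulated, so a point or two is noise).

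| Test | 5% per year | 10% per year |
|---|---|---|
| Log-rank | 42% | 64% |
| Chi-square, all follow-up | 40% | 62% |
| Chi-square at 2 years | 24% | 45% |

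**The case against.** The protocol speaks of rates. It does not say ever-or-never over all follow-up. A chi-square test fits a fixed visit equally well, and 2 years would be the natural one: TESS is compared then, and every patient has that much potential follow-up. Time point and denominator are often set in a statistical analysis plan, which is not shown here. This stands as a caution, so the all-follow-up reading above is an inference. What the protocol does fix is the test. Applied at 2 years it is nearly unbiased, but it discards later events that the schedule collects and has clearly less power (Step 5).

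A reader might infer that scoring stops at local relapse, so that the arm with more relapse must look less toxic. The documents do not support this. The late-morbidity schedule has no stop at relapse, the follow-up forms in section 10 continue to carry it, and section 13 keeps data collection going after withdrawal from treatment. The sentence on discretion after recurrence concerns management, not assessment. If relapsed patients go on being scored, morbidity from later treatment could push the comparison the other way. The direction is therefore conditional.

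A reader might also expect more deaths where there is more relapse. Section 1 reports no evidence from randomised trials that local control influences survival, while calling the effect uncertain.

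Finally, 80% v 70% is the edge of what the trial tolerates; smaller imbalances do little. And prevalence at a fixed visit is a legitimate target for graded states such as stiffness or fibrosis.

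**Conclusion.** The point holds in a limited form. A chi-square test without an assessment time suits a late outcome poorly when follow-up varies and ends at death. Read over all follow-up, its percentage is not a risk at any stated time, and the test is fair only if the arms lose observation equally.

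The size is modest: type I error of roughly 7.5% to 10% if observation ended at 80% v 70%, about 6% at 80% v 75%, and 5% with equal loss. These figures rest on constant hazards of 5% to 10% per year, uniform entry, and the assumption that observation ends at those rates, which the protocol does not state for relapse. They do not show that the trial would favour the research arm. Nor does the 2-to-6-year spread alone invalidate the test.

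This concerns a secondary outcome and leaves the primary analyses untouched. It is worth correcting because a better method is available at little cost.

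**What to change.** Replace the toxicity sentence in section 6 with wording such as:

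*Time from randomisation to first RTOG grade 3 or 4 late toxicity will be compared between arms by log-rank test and cause-specific hazard ratio, censoring at death or last assessment. Cumulative incidence at 2 years will be reported by arm with death as a competing event. Crude counts will be given as description only.*

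Keep the scheduled scores after relapse in the main analysis. Use censoring at local relapse only as a sensitivity analysis, since it discards data that the protocol plans to collect.

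The cost is one sentence and slightly more analysis work. Late morbidity, recurrence and survival are already on the follow-up forms. In the scenarios above no power is lost against the all-follow-up chi-square test. The drawback is that the cause-specific hazard ratio must be read alongside the cumulative incidence, because deaths that differ by arm affect the two differently.
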